The morbidity study population consists of those identified by the DMDC personnel databases or the 1999-2002 ATSDR survey as having lived or worked at Camp Lejeune during the period of drinking water contamination and a comparison population of active duty personnel and civilian employees sampled from Camp Pendleton. The morbidity study will evaluate the relationships between specific diseases of interest and exposure to drinking water contaminated with TCE, PCE, other chlorinated compounds, and/or BTEX compounds (i.e., benzene, toluene, ethyl benzene, and xylenes). These specific diseases of interest were selected based on a literature review of occupational and drinking water studies involving solvent exposure and include aplastic anemia, bladder cancer, brain cancer, breast cancer, cervical cancer, endometriosis, esophageal cancer, generalized skin disorders, Hodgkin's disease, infertility, kidney cancers, kidney diseases, leukemias, liver cancer, liver disease, lung cancer, lupus, motor neuron disease/ALS, multiple myeloma, multiple sclerosis, NHL, pancreatic cancer, Parkinson's disease, scleroderma, soft tissue sarcoma, and miscarriage.

This retrospective cohort morbidity study will utilize a health survey to identify the cancers and other diseases as well to obtain information on potential confounders such as smoking, alcohol consumption, and occupational exposures. Information on the self-reported conditions obtained from the survey will include the type of condition, age at

diagnosis, state of diagnosis, and contact information for the health provider who provided the diagnosis. Except for miscarriage, only diseases confirmed by medical records, death certificates or cancer registrations will be evaluated in the primary analyses. Self-reports of miscarriages will be considered “confirmed” if the respondent answers affirmatively that a positive pregnancy test was conducted before the miscarriage occurred **and** that the miscarriage was confirmed by a health provider (Axelsson 1990).

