Informed consent, either hardcopy or electronic, will be obtained from the participants (Appendix 3). The health survey will collect information on the following diseases an individual may have had that was diagnosed by a health provider: any cancer, Parkinson's disease, kidney failure and other severe kidney diseases, severe liver diseases, lupus, aplastic anemia, TCE-related skin disorders, scleroderma, multiple sclerosis, motor neuron disease/amyotrophic lateral sclerosis (ALS), infertility, endometriosis and miscarriages. Requested information about diseases other than miscarriages will include the type of cancer or other disease, date of diagnosis, hospital of diagnosis, and doctor who diagnosed the disease to facilitate the acquisition of medical record confirmation. Because medical records are usually unavailable for miscarriages, the survey will not request information to facilitate medical record confirmation of this adverse outcome. Instead, the survey will include two questions ("Did you have a positive pregnancy test before the

miscarriage occurred?” and “Was the miscarriage confirmed by a physician or other health provider?”) that have been shown to improve the accuracy of self-reported miscarriages (Axelsson 1990). If the respondent answers affirmatively to both questions, then the miscarriage will be considered “confirmed”. For cancers, state of diagnosis will also be obtained to facilitate acquisition of cancer registry data. Self-reported cancers and other diseases will be confirmed by medical records or cancer registrations. To facilitate medical record confirmation, the participant will be asked to provide a copy of the medical record to ATSDR or to sign a medical records release form allowing ATSDR to gain access to the medical record (Appendix 4). However, if the identified medical provider requests their own Health Insurance Portability and Accountability Act (HIPAA) compliant form be used, we will follow up with the participant and ask them to sign the additional form as well. The survey will also include a space so that the respondent can report other disease conditions not specifically mentioned in the questionnaire. These self-reported conditions will not be confirmed and will be evaluated only in a descriptive manner (e.g., a frequency table on self-reported “other conditions”).

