Determining the water quality at residences and workplaces at Camp Lejeune is simplified by the fact that, within each water system, the water was completely mixed so all locations served by a water system received similar levels of contamination. It is therefore only necessary to determine in which broad area of the base the residence or workplace is located. The information from the family housing records (for married active duty personnel), the unit identification codes (for single active duty personnel), the MOS code (for active duty workplaces), and the occupation code (for civilian employees), when combined with the information obtained from command chronologies, discussions with knowledgeable former Marines and current base staff, and survey information provided by the respondent, should be sufficient to identify the area of the base where a residence or workplace was located and to determine which water system served that residence or workplace.

Because of uncertainties and variabilities concerning the amount of water each individual routinely consumed (i.e., by ingestion, inhalation and dermal routes), the source of water in the field, the amount of time an individual routinely spent outside the base or in other parts of the base besides the residence, exposure misclassification bias is likely. This bias should be non-differential, i.e., not associated with disease status. However, non-

differential exposure misclassification can distort exposure-response relationships. One approach to reduce the effects of this bias on the exposure-disease relationship is to compare the group with the most certainty of being the highest exposed to the unexposed group. To assess the possible impact of this bias, sensitivity analyses will be conducted assuming different values for the sensitivity and specificity of the exposure classification.

Morbidity Study Population

Persons eligible for the morbidity study are those with accurate and complete addresses who were:

1. Marines and Navy personnel identified from the DMDC computerized personnel database as having been stationed at Camp Lejeune anytime during the period June 1975- December 1985;
2. civilians identified from the DMDC computerized personnel database as having worked at Camp Lejeune anytime during the period December 1972 to December 1985;
3. respondents and their children (who were born prior to 1986 and who are now adults) included in the 1999-2002 ATSDR survey;

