All electronically entered information obtained from surveys will be reviewed for missing data and ambiguous responses. Internal consistency and validity programs will be used to identify and correct coding and data entry errors. The web-based survey will include prompts to alert participants if they incorrectly answer or skip questions; drop down boxes that present ranges of possible answers; and electronic skip patterns that automatically skip irrelevant questions.

Data Analysis

The civilian employees will be analyzed separately from the active duty personnel

and their dependents. This is because the primary exposure to drinking water contaminants for the civilian employees is not the residence, but the workplace location. If the exposure-response relationship for a specific condition in the analysis of civilian employees is observed to be similar to that observed in the analysis of active duty personnel and their dependents, then a combined analysis may be conducted.

In the analysis of active duty personnel and their dependents, there are no dependents from Camp Pendleton. It will be assumed that dependents and active duty personnel with similar residential drinking water exposures (including no exposure) will have similar risks for a condition. In subsequent analyses, effect modification of the exposure-response relationship for a specific condition by whether the respondent was a dependent or active duty personnel will be explored.

Person-time will accumulate from the date the person first resided or worked at Camp Lejeune (or Camp Pendleton) until date of death or the date that the health surveys are mailed. The monthly average levels of contaminants in the drinking water will be used to estimate exposure. The exposure intensity (average and maximum exposure level), exposure duration, and cumulative exposure measures will be calculated. In addition, these exposure measures will be categorized using a priori meaningful cutpoints and/or quantiles based on the exposure distribution of respondents from Camp Lejeune, and cutpoints from a smoothing procedure (e.g., splines or LOESS). The monthly Monte Carlo 95% interval range for each contaminant will be taken into account during the categorization of exposure variables.

The analyses will focus on reported diseases of interest that are confirmed by medical record, death certificate, or cancer registration. However, because medical

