records are generally unavailable for miscarriages, a miscarriage will be considered “confirmed” if affirmative responses are provided to two survey questions: “Did you have a positive pregnancy test before the miscarriage occurred?” and “Was the miscarriage confirmed by a physician or other health provider?” These two questions have been found to improve the accuracy of self-reports of miscarriages (Axelsson 1990).

Poisson regression methods will be used to evaluate exposure-disease relationships, with exposure measures and potential confounding factors included in the models as independent variables. Logistic regression may be used to check the Poisson regression results. Survival analysis methods with age as the time variable may also be used to evaluate relationships between disease and continuous exposure (and confounder) variables. Exposure will be lagged to account for an appropriate latency period for each condition. For most cancers, the initial analyses will lag exposure by 10 years (i.e., a 10-year latency period). Additional analyses will explore other latency periods for each condition. Selection of risk factors for inclusion in the models as confounders will be based on a “10% change in the estimate” rule (Maldonado and Greenland 1993). Models will also be constructed that include well-known risk factors for the disease under evaluation from information obtained in the survey. Ninety percent confidence intervals will be calculated for parameter estimates.

The first confirmed diagnosis of a generalized skin disorder will be used in the analysis. For miscarriage, two approaches will be used. First, we will evaluate only the first pregnancy that occurs at the base. Second, we will include all pregnancies that occur

in the follow-up period and employ the generalized estimating equation (GEE) approach to account for non-independent outcomes arising from multiple pregnancies for the same woman. Induced abortions and ectopic pregnancies will be excluded from the analyses of miscarriage. For the GEE analyses, the logit link will be employed and the correlation structure will assume equal correlation between birth outcomes for the same woman.

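### Infertility is left on the general person-time rule, so its rate ratio can move away from 1 with no water effect if the share who tried to conceive differs between exposure groups

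*Protocol*

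**What the plan says.** Infertility is an outcome of the study. Morbidity Study Design lists it among the diseases to be evaluated ("Hodgkin's disease, infertility, kidney cancers"), and Data Collection lists it among the conditions the survey asks about ("motor neuron disease/amyotrophic lateral sclerosis (ALS), infertility, endometriosis and miscarriages"). Interpretation and Dissemination of Results treats each pairing of a contaminant with a listed disease as its own pre-specified hypothesis.

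Data Analysis gives a single rule for the denominator: "Person-time will accumulate from the date the person first resided or worked at Camp Lejeune (or Camp Pendleton) until date of death". For those still alive, the stated end point is instead the mailing ("or the date that the health surveys are mailed"). It names no exception by outcome. The model follows: "Poisson regression methods will be used to evaluate exposure-disease relationships".

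Two outcomes then receive rules of their own. For generalized skin disorders the first confirmed diagnosis counts. For miscarriage the unit becomes the pregnancy: "For miscarriage, two approaches will be used. First, we will evaluate only the first pregnancy that occurs at the base". The second miscarriage approach takes all pregnancies in follow-up with GEE, and induced abortions and ectopic pregnancies are excluded. Infertility has no such rule.

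On the make-up of the groups, Data Analysis says "there are no dependents from Camp Pendleton". Morbidity Study Population brings in the Lejeune parents, and their now-adult children, through the 1999-2002 survey. The Introduction explains that this survey concerned children born from 1968 through 1985 to mothers who lived on base during the pregnancy.

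**The concern.** Infertility is diagnosed essentially in people who are trying to have a child. A rate per person-year of everyone, from arrival to survey mailing, combines two things: how often people tried, and how often those who tried had difficulty. Only the second bears on the water.

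The protocol recognises this for miscarriage, where only pregnancies are at risk, but leaves infertility on the rule written for cancers and chronic diseases. If the exposed and reference groups differ in the share who tried to conceive, the infertility rate ratio differs from 1 even when exposure does nothing. The groups differ by design in one relevant respect: spouses and children are present only on the Lejeune side. A raised, null or lowered rate ratio would then be hard to interpret.

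**Working it through.** **The plan's own figure.** There is none to reproduce. Table 1 covers cancers only, and the protocol gives no expected infertility rate and no share of participants who tried to conceive.

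**The rules side by side.**

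| Outcome | At-risk set in Data Analysis |
|---|---|
| Miscarriage | Pregnancies, with stated exclusions |
| Generalized skin disorder | General person-time, first confirmed diagnosis |
| Infertility | General person-time, no restriction |

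**Null rate ratio.** Let λ be the rate of diagnosed infertility per year among people who try to conceive, the same in both groups (no water effect). Let q be the share of a group's person-time contributed by people who tried, and T its total person-time. Expected cases are λ·q·T, so the rate on all person-time is λ·q and

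RR(null) = (λ·qE) / (λ·qU) = qE / qU.

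With similar follow-up per person, q is simply the share of people who ever tried. The values below are assumptions:

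| Share tried, exposed | Share tried, reference | Null RR |
|---|---|---|
| 0.90 | 0.60 | 1.50 |
| 0.90 | 0.70 | 1.29 |
| 0.80 | 0.70 | 1.14 |
| 0.70 | 0.70 | 1.00 |
| 0.60 | 0.75 | 0.80 |

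If the denominator is restricted to people who tried, q = 1 in both groups and the null RR is 1.00 by construction.

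**Direction.** Three features of the design act on q or on λ:
- Spouses are present only at Lejeune. This raises the share who tried there and pushes the RR up.
- Those parents entered through a birth. This lowers their infertility and pushes the RR down.
- Lejeune children contribute childhood years without being at risk. This pushes the RR down.

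The protocol gives nothing that would settle the balance.

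**Size of the childhood part.** Take a child who first lived on base at birth. End follow-up in 2008 and use age 19 as the cut; both figures come from the assumptions under Table 1, where the average participant arrives at 19 and is followed to 2008.
- Born 1968: 2008 − 1968 = 40 years, of which 19/40 = 48% precede age 19.
- Born 1985: 2008 − 1985 = 23 years, of which 19/23 = 83% precede age 19.

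If no cases arise before 19, the crude rate among these children is multiplied by 21/40 = 0.525 and by 4/23 = 0.17, respectively. Camp Pendleton has no such group.

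**The case against.** Several points on the other side are sound.

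**The housing mechanism is weaker than it looks.** Exposure Assessment locates residences from "family housing records (for married active duty personnel), the unit identification codes (for single active duty personnel", and residence fixes the water system. A reader might infer that marital status therefore decides the water system. The protocol does not say so: it states which records locate whom, not which system served which quarters. The 1998 birth-outcome study described in the Introduction examined both Hadnot Point and Tarawa Terrace water among women in base family housing, so family housing spanned at least two systems. Civilian employees are exposed by workplace and analysed separately. This reading should not be relied on.

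**The groups may not differ much.** The Pendleton active duty sample is random, with no stated restriction on marital status. Table 1 has the average participant go from age 19 in 1980 to age 47 in 2008; being single at 19 says little about ever having tried by 47. A gap as large as 90% against 60% is therefore at the far end, and nothing in the protocol supports it. This limits the size, not the defect.

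**Adjustment may help.** Data Analysis foresees a 10% change-in-estimate rule, models with known risk factors, an optional survival analysis on the age scale, and a check of effect modification by dependent status. With fine control for age, years in which no group has cases carry no weight, so the part due to childhood and late years could largely vanish. That stands, but the age-scale analysis is optional and the confounder rule does not guarantee age control. Nor does age control remove people of reproductive age who never tried. Adjusting for covariates does not define who is at risk.

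**It could be left to a statistical analysis plan.** A detail on which the protocol is silent could be. Here the protocol states a rule, makes exceptions for two outcomes, and leaves infertility under a rule that does not fit it.

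**Conclusion.** The point holds for infertility alone. Followed as written, the protocol divides infertility cases by the person-time of everyone, including people who never tried to conceive and years outside reproductive age. With no water effect, the crude rate ratio equals the ratio of the shares who tried: 0.8 to 1.5 if that ratio lies between 0.8 and 1.5. This range is an assumption, because the protocol gives no shares. It also assumes equal infertility among those who try, similar follow-up, and no adjustment that happens to absorb the difference.

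Two stronger conclusions might be drawn and are not supported. One is that the bias must produce a rate ratio above 1; the design pulls both ways, so a null or lowered ratio is just as hard to read. The other is that the bias can be judged against the minimum detectable ratios in Table 1; these concern cancers and say nothing about infertility.

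The questionnaire (Appendix 1) is not shown, so whether it asks about attempts to conceive is unknown.

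**What to change.** Add to Data Analysis, for infertility only, wording such as:

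*The at-risk set for infertility is respondents who report ever having tried to conceive after first arriving at the base or, for those who were there as children, after reaching reproductive age. Person-time is limited to reproductive ages, with the age limits stated for men and women. Marital status will be considered as a covariate. Results will be reported with and without dependents recruited through the 1999-2002 survey.*

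Housing type should not be forced into the model: it is tied to residence, from which exposure is assigned, so forcing it could remove part of the exposure contrast.

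If the questionnaire does not already ask whether the respondent ever tried to conceive, add that item before mailing; collecting it later would mean recontacting respondents.

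Cost: a few sentences and at most one item on a survey that took 45 minutes on average in the pilot. The infertility analysis will include fewer people. Attempts recalled decades later will carry some error, and next of kin answering for deceased participants may not know. No other outcome is affected.

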In order to keep respondents informed of the latest developments at Camp Lejeune concerning the drinking water contamination and health issues, ATSDR will share with the USMC updated current addresses obtained as part of the health survey mailings; the USMC already has the names and contact information of the study participants and no other information will be provided to the USMC. The USMC is required by Congress to notify former residents and employees who were at Camp

Lejeune during the period of water contamination about the results of studies and other pertinent public health information. The USMC will follow appropriate measures to maintain the confidentiality of the contact information.

Communicating results of environmental epidemiology studies to the general public is often complicated and challenging. Scientific concepts may be difficult for the general public to understand and there may be trust issues between the community and the federal government. To overcome these challenges, ATSDR will engage its public communications staff to assist the Camp Lejeune researchers in communicating the results of the studies. Study participants will be informed of how ATSDR measured associations and the criteria used to interpret the meanings of the associations. Specifically, ATSDR will calculate incidence rate ratios and 90% confidence intervals for each exposure-disease relationship. Incidence rate ratios (RRs) compare the disease rates among various levels of exposed to the disease rate among the unexposed adjusting for confounders. Exposure-response relationships are examined by determining whether the RRs increase with increasing exposure level. If the disease rates are the same in the exposed and unexposed groups, then the RR is equal to or close to 1.0. A RR close to or equal to 1.0 indicates that there is a lack of association between the exposure and the disease in the data. If the exposed group has a higher disease rate than the unexposed (i.e., RR is greater than 1) or if there is a trend of increasing disease rate with increasing exposure, then there is an association between exposure and disease in the data. A confidence interval provides information on the precision of the RR. The width of the confidence interval reflects the amount of variability in the RR. The wider the confidence interval, the less precise and more uncertain is the estimate of the RR. The

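### Person-time is not stopped at diagnosis, so Poisson rate ratios above 1 are pulled modestly toward 1 for the commoner non-cancer conditions; the effect on cancers is negligible

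*Protocol*

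**What the plan says.** The Data Analysis section starts the clock when a person first lived or worked at Camp Lejeune or Camp Pendleton and runs it "until date of death or the date that the health surveys are mailed". These are the only two stopping events that the protocol gives.

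The same section makes Poisson regression the main method: "Poisson regression methods will be used to evaluate exposure-disease relationships". The section on interpretation and dissemination fixes the effect measure: "ATSDR will calculate incidence rate ratios and 90% confidence intervals for each exposure-disease relationship". Survival methods are optional: "Survival analysis methods with age as the time variable may also be used".

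For one outcome the text states that only the first event counts: "The first confirmed diagnosis of a generalized skin disorder will be used in the analysis". Miscarriage is handled apart, with pregnancies as the units and a logit GEE when all pregnancies are included.

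Under Data Collection, the survey asks for "the type of cancer or other disease, date of diagnosis, hospital of diagnosis" and other details for every listed disease except miscarriage. The list of conditions ends with "multiple sclerosis, motor neuron disease/amyotrophic lateral sclerosis (ALS), infertility, endometriosis and miscarriages".

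**The concern.** An incidence rate divides first events by the time during which a first event could still occur. Someone already diagnosed with a chronic disease cannot become a first case of it again, so later time does not belong in the denominator. Under the stated rule that time stays in until death or mailing.

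The surplus is not shared equally. The group with the higher disease rate has more diagnosed people and, other things equal, earlier diagnoses, so its denominator is inflated more. Its rate is understated more, and a rate ratio above 1 shrinks. The study rests on estimated rate ratios and exposure-response trends, so avoidable attenuation matters wherever the condition is common enough to produce it.

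**Working it through.** **1. The plan's own figures.** Inputs from Table 1: 160,550 Camp Lejeune and 39,000 Camp Pendleton respondents, two-sided alpha 0.10, power 90%. In the 10% column the unexposed number 39,000 + 0.10 × 160,550 = 55,055 and the exposed 0.90 × 160,550 = 144,495. The pooled two-proportion formula with continuity correction, solved for the detectable ratio, gives 2.429 at 0.02% unexposed incidence (stated: 2.43) and 1.329 at 0.24% (stated: 1.33). All 40 cells agree within 1.0%. Table 1 is not in dispute. It is used here for its range of cancer risks, 0.02% to 0.24%.

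**2. The rate ratio under the stated rule.** Let R0 be the cumulative risk in the unexposed over follow-up and RR the true rate ratio. Assume proportional hazards and the same follow-up T for everyone.

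- Cumulative hazards: H0 = −ln(1 − R0) and H1 = RR × H0.
- Exposed risk: R1 = 1 − exp(−H1) = 1 − (1 − R0)^RR.
- As written, each person contributes T, so the rates are R1/T and R0/T and their ratio is R1/R0, the risk ratio.

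T cancels, so the result depends neither on the length of follow-up nor on the shape of the hazard. For RR = 2 it reduces to 2 − R0.

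Example at R0 = 10%: for RR = 2, R1 = 1 − 0.90² = 0.19 and the ratio is 0.19/0.10 = 1.90. For RR = 1.5, R1 = 1 − 0.90^1.5 = 0.1462 and the ratio is 1.46.

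| Unexposed risk | True 1.5 appears as | True 2.0 appears as | Loss of log RR when true RR is 2.0 |
|---|---|---|---|
| 0.02% (Table 1, lowest) | 1.4999 | 1.9998 | 0.0% |
| 0.24% (Table 1, highest) | 1.499 | 1.998 | 0.2% |
| 1% (assumed) | 1.496 | 1.99 | 0.7% |
| 5% (assumed) | 1.481 | 1.95 | 3.7% |
| 10% (assumed) | 1.462 | 1.90 | 7.4% |
| 15% (assumed) | 1.442 | 1.85 | 11.2% |
| 20% (assumed) | 1.422 | 1.80 | 15.2% |

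The last column is 1 − ln(observed)/ln(2); at 10%, 1 − ln(1.90)/ln(2) = 7.4%.

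**3. Understatement of the rates themselves.** Adding a constant hazard, each rate is too low by 1 − R/H. At R0 = 10% and RR = 2, this is 1 − 0.10/0.1054 = 5.1% in the unexposed and 1 − 0.19/0.2107 = 9.8% in the exposed. At 0.24% the unexposed deficit is 0.12%.

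**4. Consequence for the optional cross-checks.** At R0 = 10% and RR = 2, Poisson as written gives 1.90. A survival model that ends at the event targets 2.00. Logistic regression gives an odds ratio of (0.19/0.81)/(0.10/0.90) = 2.11. If these checks are run, part of the spread comes only from the person-time rule.

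**The case against.** The strongest reply is about size. The protocol states no background risk for any non-cancer condition, and many of those listed are severe or specific diseases. Only confirmed cases count in the primary analyses, which lowers the relevant risk further. At 1% the shift is from 2.0 to 1.99. The bias runs toward the null, so for a ratio above 1 it cannot create an association. All of this stands, and it limits the point to commoner conditions.

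A second reply is that analysts routinely drop time after the event and that an analysis plan may say so. That may be how the study would be run. However, the protocol is not silent: it names its stopping events and leaves out diagnosis. A program written from that sentence would produce the attenuation.

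A reader might also infer more than the text supports:

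- **That the rule distorts every outcome.** It does not touch miscarriage, and at Table 1 risks the change is negligible. For rapidly fatal diseases, death soon ends the surplus time.
- **That the protocol defines every outcome as a first diagnosis.** It says so only for generalized skin disorders. For the other chronic conditions this follows from the choice of an incidence rate ratio.
- **That the Poisson results will clash with a planned survival analysis.** Survival methods are only an option, so any clash is conditional.
- **That a loss of 7% to 11% of the log rate ratio is established for some condition.** Those figures belong to assumed risks of 10% and 15%.

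**Conclusion.** The stated end of person-time is wrong for an incidence rate ratio, and its direction is clear: ratios above 1 move toward 1. The effect is negligible for the Table 1 cancers and other rare conditions. It is modest for conditions with an unexposed risk of several percent or more, where a true 2.0 appears as 1.95 at 5% and 1.85 at 15%. Infertility and endometriosis are possible candidates, but the protocol gives no figures to confirm this.

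The sizes rest on proportional hazards, common follow-up and assumed background risks; the direction does not depend on the assumed risks. The documents do not show that any conclusion of the study would be reversed. The correction is worth making because the error is avoidable and the repair nearly free.

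**What to change.** Amend the person-time sentence in Data Analysis so that, for each condition analysed by person-time, follow-up ends at the earliest of (a) the first confirmed diagnosis of that condition, (b) death and (c) the survey mailing date.

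The word confirmed matters. The primary analyses count only confirmed cases as events, so stopping at an unconfirmed report would remove time without adding an event. In the sensitivity analysis that adds diagnoses for which confirmation was not possible, end person-time at the first diagnosis counted as an event there. State that the rule does not apply to miscarriage.

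The cost is a sentence or two in the protocol and a condition-specific end date in the program. No new data are needed, since the survey already requests diagnosis dates.
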